Our study will enroll participants with at least two fingernails involved. This will allow us to use placebo in one fingernail of every participant, thus establishing the efficacy of ITA in our study by allowing us to compare placebo to ITA. In addition to efficacy assessments, we will measure changes in quality of life due to the study intervention as an outcome. Quality of life assessments will be done with the NPQ10 assessment, which is a validated assessment tool developed to measure quality of life in nail psoriasis.[14] This tool is included in Appendix B.

All fingernails not treated with placebo will undergo randomization to four groups corresponding to four concentrations of ITA under investigation (2.5, 5.0, 7.5, 10.0 mg/mL). Thus, a participant with five affected fingernails may have a different concentration of ITA used as the study intervention in each fingernail. This approach has been used in studies of ITA in other dermatologic diseases such as alopecia areata. [15] In the cited study, the lesions of subjects with alopecia areata were divided into four quadrants, corresponding to four concentrations of ITA that were injected. We believe this approach will be helpful in comparing the efficacy of different concentrations in the same patient.

SIGNIFICANCE

Psoriasis is a chronic, inflammatory condition that affects millions of people in the United States. Approximately 50% of patients with cutaneous psoriasis have nail involvement; nail psoriasis causes significant pain, and can lead to loss of manual dexterity, therefore impairing the ability to use the hands or perform work. Intralesional triamcinolone acetonide is considered one of the mainstays of treatment for nail psoriasis. By determining the lowest effective concentration of this medication for nail psoriasis, we can minimize side effects for millions of people affected with nail psoriasis worldwide.

OBJECTIVES

The primary objective of this study is to determine the lowest effective concentration of intralesional triamcinolone acetonide in the treatment of nail psoriasis.

The secondary objective is to determine that intralesional triamcinolone acetonide is effective in the treatment of nail psoriasis when compared to placebo, using the Nail Psoriasis Severity Index as a measure of improvement.

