Another secondary objective is to determine the rate and nature of side effects experienced by patients using different concentrations of intralesional triamcinolone acetonide for the treatment of nail psoriasis.

Another secondary objective is to assess baseline quality of life in patients with nail psoriasis and determine if there is a change in quality of life with the study intervention.

SUBJECT POPULATION

Inclusion Criteria:

The subject must meet ALL the criteria listed below for entry:

1. Subject must be at least 18 years of age, of either sex or transgendered individuals, and of any race;
2. Subject must have nail psoriasis that is clinically diagnosed of at least 2 fingernails.
3. Subject must be willing to give written informed consent and able to adhere to procedures and visit schedules;
4. Subject must consent to having the fingernails photographed during the study period

Exclusion Criteria:

The subject will be excluded from entry if ANY of the criteria listed below are met:

1. Subject with any clinically significant condition or situation, other than the condition being studied that, in the opinion of the investigator, would interfere with study evaluations or optimal participation in the study. This is including, but not limited to: immunodeficiency, onychomycosis, any other nail condition other than psoriasis, allergy to triamcinolone acetonide, local anesthetic, normal saline, or any other material used for procedures.
2. Subject who has received radiation therapy, chemotherapy, and/or immunosuppressive drugs within 6 months of study, and/or oral corticosteroids for >1 month within the 6 months of study (exception: inhaled steroids);
3. Subject known to have received treatment with investigational drugs or devices within 30 days prior to enrollment into this study;
4. Subject who is unwilling to abstain from any cosmetic nail treatments outside those provided by the study clinic, beyond basic nail trimming (i.e. no spa nail treatments, no nail polish use, no other topical prescription nail medication);

5. Subject who is unwilling to abstain from any medical nail treatments on their nails other than the study intervention (i.e. topical steroids, antifungal creams) for the duration of the study intervention and for duration of the washout period (if applicable);
6. Subject who is part of the staff personnel directly involved with this study or a family member of the investigational study staff

CONCOMITANT MEDICATIONS

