All concomitant medication usage from the period of 60 days prior to the trial through the trial period shall be documented and include the following information:

1. Medication
2. Indication
3. Dosage (including frequency)
4. Start / Stop date

All concomitant medication usage will be checked with respect to exclusion criteria and cross-referenced to adverse events (if any).

RESEARCH DESIGN / METHODS

Our approach is to assess the efficacy and safety of different concentrations of ITA in the treatment of nail psoriasis. A similar approach has been taken with psoriasis of the skin, and alopecia areata.[15, 16]

Hypothesis: The lowest concentration of ITA tested offers the best ratio of efficacy to safety.

Study Design: A total of 10 subjects who have nail psoriasis of at least two fingernails will be enrolled. During the screening visit, the investigator will discuss with each subject the nature of the study, its requirements and its restrictions during the Informed Consent Process.

The following will be performed at the screening visit:

- Review of inclusion/exclusion criteria
- Medical history and demographics including age, gender, history of psoriasis
- Review of medications
- Examination of the fingernails
- Possible tissue sampling (clipping the nail) to rule out onychomycosis
- X-ray of the affected hand
- Administration of a survey assessing quality of life at baseline.
- Use the study intervention (intralesional triamcinolone acetonide injections) on your fingernail(s)

Eliciting the patient history and physical exam are part of standard clinical practice.

Nail psoriasis is a clinical diagnosis. Tissue sampling may be taken if there is a question about diagnosis, or if there is a possible confounding diagnosis such as onychomycosis. X-rays of the hand may also be taken to determine if there is co-existing arthritic involvement, which is very common in nail psoriasis. Both of these events are part of standard clinical practice and are not research-related procedures. Patients who only decline to obtain x-rays won't be excluded from the study.

After completion of the informed consent process, the study site will take photos of the affected fingernails proposed for enrollment.

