Washout Period: Subjects who are using any form of treatment on their nails at the time of the screening visit may participate in the study provided that they are willing to undergo a two-month washout period. During this time, they must abstain from using any nail treatments (including, but not limited to: spa nail treatments, nail polish use, prescribed topical or systemic medications indicated for the nails, over the counter nail treatments, or any other nail intervention with the exception of routine clipping and washing.) After the washout period, the subject may be re-evaluated for participation in the study.

Enrollment and Randomization: Patients with at least two affected fingernails will be enrolled. For each participant, one fingernail will receive an intralesional injection of 0.1-0.2 mL of normal saline (placebo). The other affected fingernail(s) will receive an injection of 0.1-0.2mL of a pre-determined concentration of ITA. Four concentrations of ITA will correspond to four study groups: 2.5mg/mL, 5mg/mL, 7.5mg/mL and 10mg/mL. Participants' fingernails will be randomized such that there are approximately equal numbers of fingernails in each of the five groups (four study interventions, one placebo). To avoid bias, fingernails will be assigned to groups systematically. Fingernails will be assigned to groups in order of anatomical convention. For example, if the subject has involvement of both the thumb, forefinger and third finger of the right hand, the thumb is the first digit, so, if involved, it will be assigned first according to the table below. If a subject has involvement of fingernails of both the right and left hand, the fingernails of the right hand will be assigned before the left. The table assumes that up to 50 nails will be affected between the 10 subjects enrolled. In our clinical experience, this is a reasonable expectation. If more or fewer fingernails are involved during the enrollment period, the randomization table will be adjusted accordingly. The concentration of ITA injected will be different for each group. All other study procedures will be the same between groups.

Fingernail	Group
1	5
2	3
3	4
4	1
5	2
6	4
7	5
8	1
9	3
10	2
11	3
12	4
13	5
14	1
15	2

16	2
17	1
18	3
19	5
20	4
21	5
22	4
23	3
24	2
25	1
26	1
27	2
28	3
29	4
30	5
31	1
32	2
33	4
34	3
35	5
36	5
37	3
38	4
39	2
40	1
41	1
42	3
43	4
44	2
45	5
46	1
47	5
48	2
49	4
50	3

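### One placebo nail per participant and five roughly equal groups conflict unless nail counts are close to five, and the sentence allowing the table to be adjusted does not say which rule gives way

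*Combined protocol and SAP*

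**What the plan says.** Study Design sets the sample: "A total of 10 subjects who have nail psoriasis of at least two fingernails will be enrolled". Inclusion criterion 2 gives the same minimum, and only fingernails are treated, so a participant can contribute between 2 and 10 nails.

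Enrollment and Randomization then sets two allocation rules.

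- **Placebo rule.** "For each participant, one fingernail will receive an intralesional injection of 0.1-0.2 mL of normal saline (placebo"). The Introduction/Background says the same of the two-nail entry requirement: "This will allow us to use placebo in one fingernail of every participant". It sends all the other nails to the four triamcinolone concentrations.
- **Balance rule.** Nails are to be randomised so that there are "approximately equal numbers of fingernails in each of the five groups", placebo being one of the five.

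Nails take the rows of Table 1 one after another in anatomical order, right hand before left; group 5 in the table is placebo. On the number of rows: "The table assumes that up to 50 nails will be affected between the 10 subjects enrolled". On departures from that number: "If more or fewer fingernails are involved during the enrollment period, the randomization table will be adjusted accordingly".

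**The concern.** The placebo rule fixes the placebo total by the number of participants, while the concentration totals depend on the number of affected nails. Nothing ties the two together, so the balance rule is met only if the nail count happens to suit it. The printed table is built for the balance rule and does not enforce the placebo rule. Staff following the protocol would therefore have to break one rule or the other for many participants, and the text does not say which.

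Two things are at stake. The placebo comparison, a secondary objective, relies on each participant having a saline nail. The comparison of concentrations, which bears on the primary objective, relies on the number of nails per concentration. In addition, the list is printed in the protocol, and an adjustment with no stated rule or time leaves it open to change after assignments are known. That weakens the protection the section seeks from systematic assignment.

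**Working it through.** **Inputs.** 10 participants (Study Design). 2 to 10 affected nails each (Inclusion Criteria; fingernails only). One placebo nail per participant, the rest to four concentrations (Introduction/Background; Enrollment and Randomization). Table 1 as printed. The documents contain no sample-size calculation, so there is no power figure to reproduce.

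**1. The plan's own figure.** Table 1 has 50 rows, 10 for each of the five groups, and each of its ten consecutive blocks of five rows contains every group once. If every participant has exactly five affected nails, each takes one block: one placebo nail each and 10 nails per group. Both rules are met.

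**2. Hold the placebo rule and vary the nail count.** Let m be the mean number of affected nails.

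Placebo nails = 10 × 1 = 10, for any m.

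Nails per concentration = (10m − 10)/4 = 10(m − 1)/4, on average.

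| Mean nails m | Total nails | Placebo | Each concentration |
|---|---|---|---|
| 2 | 20 | 10 | 2.5 |
| 3 | 30 | 10 | 5 |
| 4 | 40 | 10 | 7.5 |
| 5 | 50 | 10 | 10 |
| 6 | 60 | 10 | 12.5 |
| 10 | 100 | 10 | 22.5 |

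Setting 10(m − 1)/4 = 10 gives m = 5, the only point of exact equality. The protocol defines no tolerance, so any band is an assumption. Concentration groups within 10% of placebo (9 to 11 nails) need 46 to 54 nails in total, m = 4.6 to 5.4. Within two nails (8 to 12) they need 42 to 58, m = 4.2 to 5.8. At m = 4 and m = 6 the difference is 2.5 nails, or 25%.

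**3. Hold the table and count placebo nails per participant.** The placebo rows are 1, 7, 13, 19, 21, 30, 35, 36, 45 and 47. Assign rows in sequence, with the same number of nails for each participant (table repeated after row 50 where needed):

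| Nails each | Nails per group | Exactly one placebo | None | Two |
|---|---|---|---|---|
| 3 | 6 | 4 | 5 | 1 |
| 4 | 8 | 6 | 3 | 1 |
| 5 | 10 | 10 | 0 | 0 |
| 8 | 16 | 4 | 0 | 6 |

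The groups stay equal and the placebo rule fails. With three nails each, for example, the seventh participant takes rows 19 to 21 and gets two placebo nails, and the eighth takes rows 22 to 24 and gets none.

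**4. A mean of five does not rescue the table.** If the first participant has seven affected nails and the second three, the mean is five. The first takes rows 1 to 7 and gets two placebo nails (rows 1 and 7); the second takes rows 8 to 10 and gets none. Nail counts must line up with the table's blocks, and a total of 50 does not ensure that.

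**5. Can the adjustment repair this?** No. By step 2, no rearrangement makes the five groups equal while each participant keeps exactly one placebo nail, unless m = 5. Any adjustment must choose which rule to relax, and the sentence does not choose.

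**The case against.** The strongest reply is that the protocol promises only approximate equality, calls its expectation of up to 50 nails reasonable, and provides openly for more or fewer. Much of this stands. A reader might infer that the balance rule can be met only at a mean of exactly five. That is true of exact equality alone; a mean between roughly 4 and 6 could fairly be called approximately equal.

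Three further inferences are tempting, and the documents do not support them.

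- **That nail counts will probably fall short, so the concentration groups lose nails.** The wording up to 50 hints at a ceiling, but the next sentences allow for departures either way and no distribution of nail counts is given. Above five nails the concentrations gain.
- **That precision falls by a known factor from plan.** With independent nails, √(10/5) = 1.41 would be the ratio of standard errors for a between-concentration difference at m = 3 against 10 per group. But the protocol states no planned standard error, and nails on one hand are not independent. The ratio is illustrative only, and the conclusion does not use it.
- **That people who know the assignments will edit the list during enrolment.** In the sentence, the enrolment period describes when nails are found to be involved. It does not say who adjusts the table, when, or with what knowledge. Adjusting could mean no more than adding rows at the end. The fixed anatomical order also limits the choice of nail within a participant.

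What remains is that the two rules conflict over much of the eligible range, that the table and the placebo rule disagree at every constant count from two to ten except five, and that the only remedy is unspecified.

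**Conclusion.** The point holds in this form: as written, the allocation rules cannot both be followed unless nail counts are close to five, and the protocol does not say which gives way. Under the placebo rule, a concentration group can average anything from 2.5 to 22.5 nails against 10 placebo nails across the eligible range. Under the table, groups stay equal but, at three nails each, half the participants have no placebo nail.

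This rests on 10 participants enrolled as planned, the one-placebo rule read literally, and, for the table counts, rows used strictly in sequence with a constant count per participant. The boundary of roughly 4 to 6 nails is my assumption. The criticism of the adjustment sentence is one of missing specification: it leaves room for allocation to be influenced by known assignments, but does not show that this would happen.

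**What to change.** Keep the one-placebo rule, which both the Introduction/Background and Enrollment and Randomization state, and let the balance rule yield.

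1. Replace the equal-groups statement with 10 placebo nails and an average of 10(m − 1)/4 nails per concentration, shown over a range of m.
2. Before enrolment, replace Table 1 with a locked, concealed list covering up to 10 nails for each of 10 participants (100 entries). For each participant, choose one affected nail at random for placebo. Assign the rest in random permutations of the four concentrations, starting afresh within each participant so that no concentration repeats before all four have been used.
3. Balance the starting concentrations across participants so that group totals stay as even as 10 participants allow.
4. Leave unused entries unused, and delete the sentence on adjusting the table.
5. Record which nails are affected and their baseline NaPSI before opening that participant's assignments.

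The cost is one new list and a few lines of protocol text, with no extra participants or visits. The downside is that the stated size of the concentration groups becomes less favourable if the mean nail count is below five.

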Table 1: Randomization of subjects' fingernails to groups. Groups are numbered 1-5 and correspond to concentrations of ITA such that 1=2.5mg/mL; 2=5.0mg/mL; 3=7.5mg/mL; 4=10.0mg/mL; 5=placebo.

Procedures: Injections of ITA will be administered using standard methods. Hand hygiene procedures will be performed and the administrator will use gloves. Triamcinolone acetonide, at the determined dose, will be drawn into a solution of 1% lidocaine. The nail fold of the affected nail will be cleaned with an alcohol swab. In addition to the local anesthetic given as part of the injection, the area will be anesthetized with an ethyl chloride spray immediately prior to injection using a 30 gauge needle. During injection, the participant may experience light pressure. Following injection, the wound will be covered with a bandage. A board-certified dermatologist will perform all procedures and will be present to monitor for unlikely adverse events, such as excessive bleeding.

None of these procedures differ from the current standard of care. The only aspect that will differ in the treatment of affected nails is the concentration of ITA used. However, there is no current standard of care regarding the concentration; all concentrations under investigation are part of typical clinical practice and have been validated in studies.[1] The purpose of this study is to determine the lowest effective concentration of ITA in the treatment of nail psoriasis.

The schedule of treatments is as follows:

Treatment will be performed using ITA with a frequency of once per 6 weeks +/- 1 week. A follow-up visit will be performed at 24 weeks, ending the study period.

The following will be performed at the first visit:

- Completion of Nail Psoriasis Severity Index
- Collection of survey to document subject's quality of life
- Use the study intervention (intralesional triamcinolone acetonide injections) on the subject's fingernail(s)
- Take pictures of subject's nails before and possibly after treatment
- Take an X-ray of the affected hand

The following procedures will be performed at every treatment visit after the first, and at the follow-up visit:

- Measurements of clear nail growth (in millimeters), clear nail area (in mm²)
- Completion of Nail Psoriasis Severity Index.
- Use the study intervention (intralesional triamcinolone acetonide injections) on the subject's fingernail(s)
- Take pictures of subject's nails before and possibly after treatment

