- Collection of adverse events, if there are any

The following procedures will be performed at the follow-up visit only:

- Measurements of clear nail growth (in millimeters), clear nail area (in mm²)
- Completion of Nail Psoriasis Severity Index.
- Take pictures of subject's nails
- Collection of survey to document subject's changes in quality of life since the beginning of the study intervention and subjective assessment of nail since the beginning of the study intervention

ADVERSE EVENTS AND REPORTING

Adverse event/effect (AE) assessment will be ongoing throughout the study. All adverse events shall be reported by the clinical Investigator to the Sponsor and IRB following WCMC's reporting policies.

Unanticipated Adverse Effect (UAE)

An unanticipated adverse effect is an adverse effect on health and safety caused by, or associated with, the study intervention, if that problem was not previously identified in nature, severity, or degree of incidence in the investigational plan or application, or any other unanticipated problem that relates to the rights, safety, or welfare of subjects.

The Investigator shall be responsible for determination of the causal relationship of all adverse events to the study intervention and/or procedure. The Principal Investigator is responsible for monitoring the safety of the subjects enrolled.

Any adverse events will be reviewed and analyzed by the Principal Investigator as soon as the event occurs and will be documented in the subject's binder. Any unexpected adverse reactions will be reported by telephone to the IRB within 48 hours of observing the event.

No major adverse effects are anticipated during this study; however, we will screen for severe pain (Pain \geq 8/10 on self-reported scale).

The following minor adverse effects are anticipated: cold/burning sensation, minor to moderate pain (Pain \leq 7 on VAS scale), minor swelling (edema), minor hematomas, and temporary erythema (redness). We will screen for additional possible but not expected adverse effects. If the minute treatment reaches an intolerable threshold of pain $>$ 7, the study intervention will be stopped and more anesthetic may be applied if appropriate. Such pain could result from local injection of the skin. A physician will be on site for the to assess for adverse events as needed.

POTENTIAL ADVERSE EFFECTS:	
Epidermal/Nail Response Assessed	Grading
Pain	0 = none 1 2 3 = extreme
Persistent Erythema	0 = none 1 2 3 = extreme

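### Placebo nails get normal saline and ITA nails get triamcinolone in 1% lidocaine, although the protocol says the groups are otherwise treated alike

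*Combined protocol and SAP*

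**What the plan says.** In the combined protocol and SAP, Enrollment and Randomization (under Research Design / Methods) sets up five groups of nails: four ITA concentrations and one placebo. For each participant, "one fingernail will receive an intralesional injection of 0.1-0.2 mL of normal saline (placebo", and the other affected nails receive the same volume range of ITA at the assigned concentration. The section then says that the ITA concentration differs by group and that "All other study procedures will be the same between groups".

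The next part, Procedures, describes how the ITA injection is made up: "Triamcinolone acetonide, at the determined dose, will be drawn into a solution of 1% lidocaine". It treats this lidocaine as working anesthesia and not merely as a diluent. The ethyl chloride spray is introduced with the words "In addition to the local anesthetic given as part of the injection". No separate preparation is given for the placebo, and no section says that the saline contains lidocaine.

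Three other places matter:

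- Objectives makes ITA versus placebo on NaPSI a secondary objective.
- Adverse Events and Reporting and Data Analysis grade pain and burning/cold sensation from 0 to 3 at the treatment visits.
- The follow-up visit collects a "subjective assessment of nail since the beginning of the study intervention".

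**The concern.** A placebo isolates the drug only if it matches the active injection in everything else. Here the named placebo lacks a component of the active injection, and that component is a local anesthetic. The contrast labeled ITA versus placebo is, as written, ITA plus lidocaine versus saline.

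The outcomes closest to an injected anesthetic are pain and burning on injection. Both are anticipated adverse effects and both are graded. If placebo nails sting more because they received no lidocaine, a reader comparing nails could take ITA to be better tolerated than it is. The design is also within-participant, so a person who feels both kinds of injection has a direct basis for telling them apart.

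**Working it through.** **Composition, side by side**

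| Component | Placebo nail | ITA nail | Source |
|---|---|---|---|
| Steroid | none | 2.5, 5, 7.5 or 10 mg/mL | Enrollment and Randomization |
| Carrier | normal saline | 1% lidocaine | Enrollment and Randomization; Procedures |
| Volume | 0.1-0.2 mL | 0.1-0.2 mL | Enrollment and Randomization |
| Ethyl chloride spray | yes, through the sameness sentence | yes | Procedures |

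Two rows differ between placebo and ITA nails. The sameness sentence allows for one.

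**Lidocaine per injection**

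A 1% solution contains 10 mg/mL.

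- ITA nail: 10 mg/mL x 0.1 mL = 1 mg, and 10 mg/mL x 0.2 mL = 2 mg. These are upper figures, because the final strength is lower if 1% is the strength before mixing.
- Placebo nail: 0 mg, taking the text as written.

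**How many nails and injections**

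In the randomization table, group 5 (placebo) is assigned to fingernails 1, 7, 13, 19, 21, 30, 35, 36, 45 and 47. That is 10 of 50, or 20%. Treatment every 6 weeks with follow-up at week 24 suggests four treatment visits (weeks 0, 6, 12 and 18), which is my assumption. Then 10 x 4 = 40 of 50 x 4 = 200 injections would carry no injected anesthetic. The 20% share does not depend on the number of visits.

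**Which comparisons this reaches**

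1. *Among ITA concentrations.* All four groups have the lidocaine carrier, so the mismatch drops out. The primary objective is touched only where placebo serves as the reference for calling a concentration effective.
2. *ITA versus placebo on NaPSI.* The contrast contains two components, but nothing in the document suggests that lidocaine changes NaPSI. No effect is shown and none is claimed.
3. *Pain and burning grades.* Injected anesthetic bears directly on these. Grades from placebo and ITA nails are not on an equal footing, and a summary over all nails mixes carrier with drug.
4. *Subjective nail assessment.* By the enrollment text, each participant has one saline nail and at least one ITA nail. A difference in sensation could identify the saline nail before this assessment at follow-up. The document gives no rate for this.

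**The case against.** The strongest reply is that the placebo description may simply be incomplete. Enrollment and Randomization does not mention lidocaine for the ITA nails either. The carrier appears only in Procedures, and if other procedures are shared, the lidocaine may have been meant for placebo nails too. The text does not exclude this. But the preparation sentence concerns triamcinolone, of which the placebo has none, and whoever prepares the injections from this text would draw up saline alone. If lidocaine was intended, the protocol still needs to say so.

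It is also fair that no placebo-versus-ITA test of pain is planned. Data Analysis tests changes from baseline in adverse effect intensity with the Wilcoxon signed-ranks test, and the side-effect objective concerns the different ITA concentrations. The pain problem is therefore one of interpretation and pooling, not of a planned test gone wrong.

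A reader might infer more than the documents support in four respects:

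- *A second sameness claim.* Procedures says "The only aspect that will differ in the treatment of affected nails is the concentration of ITA used". It follows a statement that the procedures match standard care and precedes one that no standard exists for the concentration. In context it compares the study with usual care, not one group with another. The contradiction rests on the Enrollment and Randomization sentence alone.
- *Biased efficacy.* Nothing shows that lidocaine alters NaPSI or clear nail growth.
- *More stopped injections on placebo nails.* When pain exceeds 7, "the study intervention will be stopped and more anesthetic may be applied if appropriate". Placebo nails could reach that point more often, but no pain rate by carrier is given, and all nails are meant to have the spray.
- *A broken blind.* The plan describes no blinding procedure, so recognizing the placebo nail would breach no stated rule. Nor is the subjective assessment among the efficacy measures in Data Analysis.

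**Conclusion.** The point holds within limits. Followed as written, the protocol gives placebo nails no injected anesthetic and ITA nails up to 1-2 mg of lidocaine per injection, while stating that the groups otherwise have the same procedures. This affects the 20% of nails allocated to placebo and every comparison or summary of pain and burning that includes them. It may also give participants a sensory cue to which nail is placebo.

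The size of any effect on pain, burning or subjective ratings cannot be derived from the documents. The conclusion assumes that normal saline means saline without lidocaine, and that the four ITA preparations have the same final lidocaine strength, which the protocol does not spell out. The mismatch is worth correcting because a matched placebo is cheap and would let the placebo contrast isolate triamcinolone. It does not call the comparison of concentrations into question.

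**What to change.** Prepare the placebo in the same lidocaine carrier as the ITA injections, without triamcinolone, and state one final lidocaine strength for all five preparations. No new eligibility screen is needed, since the Exclusion Criteria already cover "allergy to triamcinolone acetonide, local anesthetic, normal saline, or any other material used for procedures". The cost is a few sentences of protocol text and a changed placebo preparation. The small downside is that placebo nails receive an injected anesthetic.

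If saline alone is kept:

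- correct the sameness sentence in Enrollment and Randomization to name the carrier as a second difference;
- describe the placebo contrast as ITA in lidocaine versus saline;
- limit pain and burning summaries to the ITA groups, which requires these effects to be graded per nail.

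That alternative costs only wording and, if grades are not already kept per nail, a change to the adverse effect form. It leaves the possible sensory cue in place.
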